## 3 Data Sources

The data source for this study is the US Medicare claims and enrollment databases in the Centers for Medicare & Medicaid Services (CMS) Shared Systems Data (SSD), for elderly persons aged 65 years and older in the US, with continuous Medicare Fee-for-Service (FFS) coverage only. Demographics and information on death is derived from the enrollment databases. Information on vaccinations, health covariates, preventive services, and outcomes are derived from Medicare Part A (inpatient) and Part B (outpatient settings and providers). Medicare claims data undergo three stages of processing: enumeration, adjudication, and final payment. CMS Medicare SSD, which consists of claims sourced after enumeration, will be used in this study. SSD is updated daily and is over 80% complete within 30-70 days depending on the care setting and outcome. Information on nursing home residency status is derived from clinical assessment of residents in the Minimum Data Set (MDS). Additionally, we will capture nursing home characteristics through the Nursing Home Compare (NHC) dataset and COVID-19 Nursing Home COVID-19 public file reported to the CDC and provided by CMS. For each person in the study, administrative claims from all care settings will be linked to create a longitudinal record of their health encounters, diagnoses, and drug prescriptions.

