#### **Exclusion Criteria**

- I. Individuals less than 65 years of age at the time of bivalent booster vaccination.
- II. Individuals vaccinated with multiple brands on the same day or multiple vaccinations (same/different brand) within 3 days of each other
- III. Individuals who had a dialysis claim (identified as a type of bill code 72x) in the 90 days prior to event; excluded as we expect these patients to have a greater mortality risk than the typical Medicare beneficiary
- IV. Individuals on hospice care on vaccination date; excluded because high fatality rate amongst this group may violate SCCS methods assumptions.
- V. Individuals who reside in a nursing home at any point between August 31, 2022 and vaccination date.
- VI. For case population only:
  - a. Individuals that do not contribute follow-up time to both risk and control intervals. If individuals disenroll or reach the end of the study period during the risk window prior to accumulating any time for post-vaccination control intervals, they will be excluded.

- b. Individuals who had a diagnosis of a stroke outcome during the outcome-specific clean window.
- c. Individuals who had a diagnosis of COVID-19 in the 30 days prior to the stroke outcome.
- d. Individuals who reside in a nursing home at any point between vaccination date and outcome date.

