### 5.3.3 Follow-Up Analysis II: Nursing Home Residents

Nursing home residents are studied separately from the 65+ year old population because they are considered a higher risk population for the outcomes.

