### 5.4.1 Observation Period/Follow-Up

For each individual, the observation period will start from the day following bivalent booster vaccination date, i.e., day 1 after vaccination and until the earlier of 90 days post-vaccination, disenrollment, administration of a subsequent mRNA COVID-19 vaccine, death or study period end. Day 0 (date of vaccination) is not included in the observation period since we would not be able to attribute stroke outcomes on this day to the exposure.

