### 5.4.2 Risk Window

The risk interval is defined as the time during which risk of a stroke outcome is hypothesized to be related to vaccination based on biological plausibility and clinical input (Table 2). The selected risk intervals for all stroke outcomes are days 1-21 and days 22-42. The 1-21 day risk interval was selected to align with the definition of stroke as used by the CDC in their RCA. The 22-42 day risk interval is selected to assess any difference in risk during this period, and to avoid any biases in risk estimates that may arise from a carryover effect from the vaccine exposure into the control interval. Implementing a split window addresses concerns that risk of the outcomes may not be constant throughout the risk period. Risk intervals will not be split further in an effort to preserve statistical power.

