### 5.4.3 Control Window

The post-vaccination control interval is defined as all follow-up time during the observation period following a vaccination that is outside of the risk interval(s) until the earlier of 90 days post-vaccination, disenrollment, subsequent mRNA COVID-19 vaccination, death, or study period end. Individuals who only accrued data during the risk intervals will be excluded from the analysis.

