## 5.5.2 Primary Analysis: SCCS with Post-vaccination Control Intervals

### 5.5.2.1 Incidence Rate Ratio (IRR) Estimation

For the primary SCCS analysis, the rates of the stroke outcomes following the bivalent booster doses dose will be evaluated by brand. This analysis will compare the stroke outcomes rates in the risk and control intervals using a conditional Poisson regression model. A Farrington-adjusted SCCS model will be implemented that adjusts for the reduced observation time that can occur from the occurrence of an outcome. We assume that only one incident event can occur in the observation period. Therefore, we only consider the first observed outcome.

$$\log(E(Y|X)) = \beta_1(\text{risk window}_1) + \beta_2(\text{risk window}_2) + \log(t) + \text{strata}(\text{pateint id})$$

$Y = \text{Stroke Outcome}$

$\text{risk interval} = \text{indicator for exposure}$

$t = \text{interval}$

$\text{patient id} = \text{term identifying the patient}$

Under this model, the null and alternative hypotheses for each risk window can be written as, respectively:

$$H_0: e^{\beta_1} = 1 \quad H_a: e^{\beta_1} \neq 1$$

$$H_0: e^{\beta_2} = 1 \quad H_a: e^{\beta_2} \neq 1$$

Where,  $e^{\beta_1}$  and  $e^{\beta_2}$  will be interpreted as the IRR for the stroke outcomes in the risk intervals compared to the control intervals. Thus, statistical significance of the coefficient on the risk interval variable at a pre-specified level will indicate a statistically significant association between COVID-19 vaccination and the stroke outcomes. Statistical significance will be determined using 95% CIs of IRRs and two-sided p-values ( $p \leq 0.05$ ).

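### The case-only nursing-home exclusion looks back further the later the stroke occurs while the person-time stays in the model, which pushes the null IRR modestly above 1; report the SCCS with and without it.

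*Protocol*

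**What the plan says.** Two nursing-home rules apply to the main cohort in Section 5.3.1. Criterion V, for everyone vaccinated, excludes "Individuals who reside in a nursing home at any point between August 31, 2022 and vaccination date". Criterion VI.d, for cases only, excludes "Individuals who reside in a nursing home at any point between vaccination date and outcome date". Section 5.3.2 has the same pair as VI and VII.d.

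On timing, Section 5.4.2 states: "The selected risk intervals for all stroke outcomes are days 1-21 and days 22-42". Section 5.4.3 defines control time as "all follow-up time during the observation period following a vaccination that is outside of the risk interval(s"), which is days 43-90 at full follow-up. Section 5.4.1 runs observation "until the earlier of 90 days post-vaccination, disenrollment, administration of a subsequent mRNA COVID-19 vaccine, death or study period end". Nursing-home entry is not in that list, nor in its influenza counterpart in Section 5.4.1.1.

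On the model, Section 5.5.2.1 states: "A Farrington-adjusted SCCS model will be implemented that adjusts for the reduced observation time that can occur from the occurrence of an outcome". On the source of residence status, Section 3 states: "Information on nursing home residency status is derived from clinical assessment of residents in the Minimum Data Set (MDS").

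**The concern.** Criterion V has already removed anyone with a nursing-home stay from August 31, 2022 to vaccination, so VI.d acts only on stays that begin later. Having been in a nursing home since vaccination is a status that starts near zero and can only accumulate. The other look-backs for cases have a fixed length: 90 days for dialysis, 365 days for the clean window, 30 days for COVID-19. VI.d is the one that grows with the day of the event.

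The SCCS compares event counts with time at risk within a person. Someone who enters a nursing home on day e can no longer contribute a stroke after day e, yet days e to 90 still count as time in which a stroke could have been observed. Because the comparator is always the later period, the loss falls more heavily on it, and both IRRs rise.

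Nothing planned corrects this. The Farrington adjustment deals with observation shortened by the outcome, not with cases removed for something that happened before it. The sensitivity analyses in Section 5.5.4 cover seasonality and positive predictive value. What is at stake is the reading of a small elevated IRR in a study meant to confirm or dismiss a safety signal.

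**Working it through.** The protocol gives no figure for this exclusion, so there is none to reproduce. Its one bias figure, for claims delay in Section 5.2, recomputes correctly: 100/90 - 1 = 11.1%.

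**Inputs from the protocol.** Risk windows are days 1-21 and 22-42; control time is days 43-90 (48 of 90 days, 53%). The mean look-back under VI.d is the mean event day: 11, 32 and 66.5 days.

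**Assumptions.** The true IRR is 1, the within-person stroke rate is flat, follow-up is complete, and a share p of would-be cases enters a nursing home by day 90 at an even pace. p is not in the protocol; 2% to 10% is shown.

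**Where the removed strokes fall.** Removal on day t is proportional to t, and the days 1 to 90 sum to 4,095.
- Days 1-21: 21 × 11 = 231, or 6%.
- Days 22-42: 21 × 32 = 672, or 16%.
- Days 43-90: 48 × 66.5 = 3,192, or 78%.

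If follow-up stops at day 60, the control share is 18 × 51.5 / 1,830 = 51%, against 18/60 = 30% of the time.

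**Apparent IRR.** This is the retained share in the risk window over that in the control window:
- Days 1-21: (1 - p × 11/90) / (1 - p × 66.5/90)
- Days 22-42: (1 - p × 32/90) / (1 - p × 66.5/90)

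| p | Days 1-21 | Days 22-42 |
|---|---|---|
| 2% | 0.9976/0.9852 = 1.013 | 0.9929/0.9852 = 1.008 |
| 5% | 0.9939/0.9631 = 1.032 | 0.9822/0.9631 = 1.020 |
| 10% | 0.9878/0.9261 = 1.067 | 0.9644/0.9261 = 1.041 |

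A conditional-likelihood SCCS simulation with 2,000,000 cases per scenario agrees: 1.031 and 1.023 at p = 5%, 1.069 and 1.039 at p = 10%. Without VI.d, the simulated IRRs return to 1.00. Entry that is front-loaded or delayed changes the values little (days 1-21 at p = 5%: 1.032 and 1.033). Follow-up ending at day 60 gives 1.023 at p = 5%.

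**Scale against precision.** Assume 5,000 cases (the protocol gives no count). Then 5,000 × 21/90 = 1,167 fall in days 1-21 and 5,000 × 48/90 = 2,667 in control time. The SE of the log IRR is √(1/1,167 + 1/2,667) = 0.035. At the 80% power and two-sided 0.05 of Section 5.6, the minimum detectable IRR is about exp(2.8 × 0.035) = 1.10.

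**If the stroke rate rises k-fold after entry.** Without VI.d, the apparent IRR for days 1-21 is [1 + (k-1)p × 11/90] / [1 + (k-1)p × 66.5/90]. With k = 2 (an assumption): 1.0061/1.0369 = 0.97 at p = 5%, and 1.0122/1.0739 = 0.94 at p = 10%.

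**Censoring at entry instead.** This gives 1.00 if entry is unrelated to stroke. If 20% of strokes lead to entry a few days later (an assumption, simulated at p = 5%), it gives about 0.65 for days 1-21 and 0.84 for days 22-42.

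**The case against.** A reader might infer that the bias is as large as the effects the study can detect. The figures do not support that: 1.013, 1.032 and 1.067 all lie below about 1.10, and the formula reaches 1.10 only at p near 15%. Section 5.2 already tolerates up to 11% from claims delay. The size also rests wholly on an assumed p. Excluding earlier nursing-home residents, hospice and dialysis patients may keep p low, and the protocol leaves open whether a short post-acute stay counts as residing. All of this stands. What remains is that the claims-delay bias is stated in the plan and this one is not, and that they add in the same direction.

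A reader might also infer that VI.d serves no purpose beyond this differential loss. That is not so. Section 2 targets people who do not live in a nursing home, and Section 5.3.3 says of residents that "they are considered a higher risk population for the outcomes". VI.d carries that restriction forward to the outcome date. The difficulty is that it does so by removing events without the matching time.

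The third tempting inference is that deleting VI.d cures the problem. It does so only if entry leaves a person's stroke rate unchanged. If the rate rises, deletion adds events to the control window and can mask a risk, by an amount similar to the inflation at issue. Section 5.3.3 compares groups and does not settle what happens within a person, but the possibility is fair and it limits the fix.

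Finally, that most removed strokes come from control time holds at near-full follow-up. It weakens to about half at 60 days, although the control window still loses more than its share.

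**Conclusion.** The point holds in a limited form. Under a flat within-person stroke rate, VI.d and VII.d push the null IRR above 1 in both risk windows, more so in days 1-21. The size is about 1.01 to 1.07 for days 1-21 and 1.01 to 1.04 for days 22-42 if 90-day nursing-home entry among would-be cases is 2% to 10%. That range is an assumption, as is the case count behind the 1.10 benchmark. The bias alone is unlikely to produce a detectable effect, but it is unacknowledged, adds to the claims-delay bias, and bears on what a small elevated IRR can support. The protocol does not show that VI.d is worthless or that removing it gives an unbiased answer.

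**What to change.** Define community residence once, at vaccination, using criterion V of Section 5.3.1 and criterion VI of Section 5.3.2. Run the SCCS without VI.d and VII.d and report it side by side with the version that applies them. Report the number of cases those criteria remove in days 1-21, 22-42 and 43-90, which replaces the assumed p with data.

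Do not simply end observation at nursing-home entry, because a stroke can itself lead to entry and the resulting error may be far larger than the one being repaired.

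The cost is one further model run per outcome and brand and a small table. The downside is that the added analysis includes some strokes after nursing-home entry and is biased modestly downward if stroke risk rises then. The two results should therefore be read together as a bracket.

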### 5.3.2 Secondary Analysis II: Influenza Vaccines

Eligible vaccinated individuals for the secondary analysis – influenza vaccination are persons who received a high-dose or adjuvanted influenza vaccine, and who did not receive a same day concomitant bivalent booster. All eligible vaccinated individuals will be used for the attributable risk (AR) calculation.

#### **Inclusion Criteria**

- I. Medicare beneficiaries enrolled in Part A (hospital insurance) and Part B (medical insurance) during the study observation period
- II. Continuous enrollment will be required from 365 days prior to vaccination date until the earlier of 90 days post-vaccination, disenrollment, administration of any subsequent influenza vaccine, administration of any mRNA COVID-19 vaccine, death or study period end.
- III. Received a high-dose or adjuvanted influenza vaccine in the observation period but not before the study start date, August 31, 2022.
- IV. For case population only, had a record of a stroke outcome diagnosis during the study observation period.

#### **Exclusion Criteria**

- I. Individuals less than 65 years of age at the time of influenza vaccination.
- II. Individuals vaccinated with multiple brands of an influenza vaccine on the same day or multiple vaccinations (same/different brand) within 3 days of each other
- III. Individuals who receive a concomitant bivalent booster vaccination
- IV. Individuals who had a dialysis claim (identified as a type of bill code 72x) in the 90 days prior to vaccination; excluded as we expect these patients to have a greater mortality risk than the typical Medicare beneficiary
- V. Individuals on hospice care on vaccination date; excluded because high fatality rate amongst this group may violate SCCS methods assumptions.
- VI. Individuals who reside in a nursing home at any point between August 31, 2022 and vaccination date.
- VII. For case population only:
  - a. Individuals that do not contribute follow-up time to both risk and control intervals. If individuals disenroll or reach the end of the study period during the risk window prior to accumulating any time for post-vaccination control intervals, they will be excluded.

- b. Individuals who had a diagnosis of a stroke outcome during the outcome-specific clean window.
- c. Individuals who had a diagnosis of COVID-19 in the 30 days prior to the stroke outcome.
- d. Individuals who reside in a nursing home at any point between vaccination date and outcome date.

### 5.3.3 Follow-Up Analysis II: Nursing Home Residents

Nursing home residents are studied separately from the 65+ year old population because they are considered a higher risk population for the outcomes.

#### **Inclusion Criteria**

- I. Medicare beneficiaries enrolled in Part A (hospital insurance) and Part B (medical insurance) during the study observation period
- II. Continuous enrollment will be required from 365 days prior to vaccination date until the earlier of 90 days post-vaccination, disenrollment, administration of a subsequent mRNA COVID-19 vaccine, death or study period end.
- III. The resident must have been residing in a nursing home since August 31, 2022 and until vaccination date. (Gaps in NH stay are permitted unless they are discharged back to the community or death).
- IV. The resident must have an MDS assessment in the 183 days prior to outcome date with no assessment records suggesting official discharge within the 100 days prior to study start date, and reside in a nursing home with available data in NHC.
- V. Received a bivalent booster in the observation period but not before the bivalent booster EUA, August 31, 2022.
- VI. For case population only, had a record of a stroke outcome diagnosis during the study observation period.

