## Version Control

Name	Date	Version	Description
Acumen, LLC	January 24, 2023	0.1	Drafting
Acumen, LLC	February 7, 2023	0.2	Addition of a possible influenza vaccine analysis, refinement of study objectives, updated outcome definitions to include adjustments and exclusions, adjusted the prior COVID-19 definition
Acumen, LLC	February 9, 2023	0.3	Cleaned up language, restricted NH population to long term care residents only
Acumen, LLC	February 13, 2023	0.4	Moved NH analysis to follow-up, edited study population exclusions, elaborated on analysis purposes, reformatted
Acumen, LLC	February 22, 2023	0.5	Removed prior COVID-19 subgroup and clarified exclusion/censoring criteria. Made 508 compliance edits.

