## 2.3 Follow-Up Analysis

We have specified two follow-up analyses to occur at a later point in time. The objectives of these analyses are to evaluate:

- I. The risk of stroke outcomes (as defined in Section 4.3) following exposure to the Pfizer-BioNTech COVID-19 Vaccine, Bivalent and Moderna COVID-19 Vaccine, Bivalent booster doses among Medicare long-term stay nursing home residents age 65+.
- II. The risk of hemorrhagic stroke (HS), non-hemorrhagic stroke (NHS), and the combined outcome of non-hemorrhagic stroke or transient ischemic attacks (NHS/TIA) following exposure to the Pfizer-BioNTech COVID-19 Vaccine, Bivalent and Moderna COVID-19 Vaccine, Bivalent booster doses (by brand) among Medicare beneficiaries 65+ using an alternate definition of care setting (including the outpatient emergency department (OP-ED) setting in addition to the originally specified inpatient (IP) setting (see Section 4.3 for primary setting definitions).

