## 5.2 Study Period

The study period will start on the date of the emergency use authorization for bivalent boosters in the U.S. (August 31, 2022) and will end on the date through which complete claims data (defined as at least 90% complete) and adequate power to assess risk estimation are available for the data source at the time of study initiation.

The completeness threshold was selected to balance the potential bias due to partially accrued observation of post-vaccination control intervals versus risk intervals, and a reasonable delay of the analysis. The 90% completeness is likely to overestimate relative risk by 10% or less. Assuming that outcome observation delays are accurately estimated from historical data, a 90% completeness threshold limits the difference in observation of outcomes in risk intervals (at most 100% complete) versus control intervals (at minimum 90% complete). If the true RR is 1, the maximum bias due to observation delay is  $(100\%/90\%)-1=11\%$ . However, in practice risk and control interval completeness will fall between 100% and 90% and we expect the potential bias due to claims delay to be smaller.

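### The nursing-home inclusion criteria set no minimum length of stay, so short stays begun just before August 31, 2022 can enter an analysis whose objective is long-term stay residents

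*Protocol*

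**What the plan says.** Section 2.3 (I) gives the target population as "booster doses among Medicare long-term stay nursing home residents age 65" and over. The version log, which is drafting history and shows intent only, records that an early revision "restricted NH population to long term care residents only".

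The cohort is built in section 5.3.3 (headed Follow-Up Analysis II, although sections 2.3 and 5.5.7 number it I). Two inclusion criteria carry the residence rule:

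- Criterion III: "The resident must have been residing in a nursing home since August 31, 2022 and until vaccination date". A parenthesis adds: "Gaps in NH stay are permitted unless they are discharged back to the community or death".
- Criterion IV: "The resident must have an MDS assessment in the 183 days prior to outcome date", together with "no assessment records suggesting official discharge within the 100 days prior to study start date", and a facility with Nursing Home Compare data.

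Section 5.2 fixes study start at August 31, 2022. Section 5.3.1, exclusion V, removes from the primary cohort anyone who lived in a nursing home at any time from that date to vaccination. Section 5.5.7 applies the methods of section 5.5.2 to the nursing-home cohort. These include the attributable risk, which is divided by all eligible beneficiaries or their follow-up.

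**The concern.** An objective restricted to long-term stay needs a rule that measures stay. Section 5.3.3 neither defines the term nor sets a threshold. A recent, possibly temporary, admission can therefore be analysed under a long-term stay label.

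The order of the windows makes this more than a labelling matter. Control time (days 43 to 90) always follows the risk windows (days 1 to 21 and 22 to 42). If a newly admitted resident's stroke risk declines with time since admission, more strokes fall in the early window with no vaccine effect. The seasonality adjustment in section 5.5.4.1 works on calendar months and would not correct this.

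A second, smaller problem lies in criterion IV. The MDS look-back counts from the outcome date, yet the criterion is not limited to cases, as criterion VI is. People without a stroke have no outcome date, so the criterion cannot be evaluated for most of the attributable-risk denominator.

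**Working it through.** The protocol gives no sample size, stay-length or composition figure for this cohort, so there is no stated number to reproduce.

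**1. The criteria applied literally.** The discharge look-back runs from May 23, 2022 (August 31 minus 100 days) to August 31.

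| Resident | Criterion III | Criterion IV | Stay at dose |
|---|---|---|---|
| Admitted Aug 29, 2022; no earlier nursing-home discharge; MDS Sep 5; dose Sep 12; stroke Oct 2 | pass | pass | 14 days |
| Same, but nursing-home discharge on Jul 1, 2022 | pass | fail | 14 days |
| Admitted Jan 1, 2020; dose Sep 12, 2022 | pass | pass | 985 days |
| Admitted Sep 2, 2022; dose Dec 20, 2022 | fail | not decisive | 109 days |

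The 100-day clause removes only people with a recent earlier nursing-home discharge. Someone who lived at home throughout those 100 days passes it. The exclusion criteria of section 5.3.3 do not remove a resident who goes home after vaccination. The last person in the table is also outside the primary cohort through section 5.3.1, exclusion V.

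**2. Stay guaranteed at vaccination** = dose date minus August 31, 2022: 0 days on August 31, 15 on September 15, 30 on September 30, 61 on October 31, 91 on November 30, and 100 from December 9.

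**3. Possible mix (all inputs assumed; none is in the protocol).** Let f be the short-stay share of admissions (50 to 90%), with exponential stays of mean m_s = 20 to 30 days (short) and m_l = 500 to 800 days (long). Among people present on August 31 who remain until a dose L days later, the short-stay share is

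s = f·m_s·exp(−L/m_s) / [f·m_s·exp(−L/m_s) + (1−f)·m_l·exp(−L/m_l)].

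Example at L = 0, f = 0.9, m_s = 30, m_l = 500: 27 / (27 + 50) = 35.1%.

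**4. Effect on the IRR for days 1 to 21 with no vaccine effect.** Let k be the ratio of the short-stay stroke rate in days 1 to 21 to that in days 43 to 90. Then null IRR = 1 − s + s·k = 1 + s(k − 1). This takes control-window rates as equal in the two groups; otherwise s must be the short-stay share of control-window events.

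| L (days) | s, assumed range | Null IRR, k = 1.5 |
|---|---|---|
| 0 | 2.4 to 35.1% | 1.01 to 1.18 |
| 14 | 1.2 to 25.8% | 1.01 to 1.13 |
| 45 | 0.3 to 11.6% | 1.00 to 1.06 |
| 75 | 0.1 to 4.9% | 1.00 to 1.02 |

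At k = 2 each excess over 1 doubles, giving upper ends of 1.35, 1.26, 1.12 and 1.05. At k = 1 there is no bias. August 31 is the authorization date itself, so L = 0 is a limiting case. The pooled IRR averages over all dose dates, and the protocol does not give their distribution.

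**The case against.** The criteria do favour long stays. They take people present on one date, keep only those who remain until vaccination, and drop anyone discharged to the community before it. Long-stay residents are the majority in every scenario above, and increasingly so for later doses. This stands. A reader might infer that the rule fails to select long-stay residents, or that the objective is answered in a post-acute population. The protocol supports neither.

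The bias mechanism is not in the protocol either. No section says that residents' stroke risk falls after admission, and section 5.3.3 justifies the separate analysis by higher risk, not by stability. Existing exclusions also remove some recent post-acute cases: the 365-day clean window for the same outcome; in Appendix Table A, stroke sequelae or history codes within 365 days and COVID-19 within 30 days for all outcomes; and, for every outcome except hemorrhagic stroke, I48* within 365 days and I21* within 28 days. The k values make no allowance for these. An upward bias is therefore conditional and cannot be asserted as fact. For scale, section 5.2 puts the maximum bias from claims delay at 11%, in the same direction.

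It may be said that a SAP can hold the derivation of long-stay status. It can hold the MDS algorithm, but the protocol already fixes the eligibility rule, and an analysis that follows it as written admits the 14-day resident.

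A reader might also take the loss of residents admitted after August 31 as a bias. Estimation is within persons, so leaving them out narrows coverage and does not by itself distort the IRR.

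**Conclusion.** The point holds as a mismatch between objective and eligibility rule in one follow-up analysis. Criteria III and IV contain no minimum stay, and 100 days' residence is guaranteed only for doses from December 9, 2022. That conclusion needs only the protocol's dates.

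The consequence for the IRR is conditional. It requires short-stay residents in the cohort and a risk that declines after admission, and the protocol quantifies neither. Under the assumed ranges the upward bias is mostly modest, concentrated in the earliest doses and small by 75 days. The largest values need 90% of admissions to be short-stay. No primary or secondary result is touched.

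The look-back defect is separate and needs no assumption: a criterion tied to the outcome date cannot be applied to non-cases in the attributable-risk denominator.

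**What to change.** - Add to section 5.3.3 a stated minimum cumulative nursing-home stay by the vaccination date, verified from MDS entry and discharge records, with gaps handled as now. One hundred days would match the figure already in criterion IV, but the protocol nowhere sets it as a minimum stay, so the sponsor should confirm and justify the threshold.
- Anchor the MDS assessment look-back on the vaccination date, so that one rule serves cases and non-cases.
- Optionally, drop the August 31 residence requirement, so that later admissions who reach the threshold before vaccination become eligible. This changes coverage and is not needed to repair the mismatch.

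The cost is protocol wording and use of MDS data, which section 3 already names as the source for residency status. The analysis is planned for a later point, so the change can precede it. The downside is the loss of some early-vaccinated recent admissions, partly offset if later admissions are allowed in.
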